#### **4.2.1. Adverse Events (AE)**

Solicited AEs within 7-days post vaccination and unsolicited AEs within the 28-day period following the vaccination are collected only for the Safety Subset. SAE are collected for all participants.

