## 5.2. SAFETY

Safety analyses for the second and third RSV season will be performed similarly to the first RSV season (see Section 4.2), based on the FAS. The analysis of solicited and unsolicited AEs will be restricted to the Revaccination Subcohorts.

For the analysis of serious AEs (SAEs) the entire FAS will be used. **For participants who will not receive a revaccination**, all SAEs will be reported from administration of study vaccine on Day 1 until the end of the first RSV season (or 6 months after vaccination, whichever comes later). In addition, SAEs classified as related to the study vaccine, SAEs resulting in death, (S)AEs resulting in study discontinuation, and (S)AEs resulting from procedures and non-investigational (concomitant) Janssen products will be collected during the entire study for all participants. For these participants, SAEs associated with ARIs and complications related to ARIs that classify as SAEs will be collected from the Day 365 (Month 12) visit until the end of the second RSV season, from the end of the second RSV season until the Day 730 (Month 24) visit, and from the Day 730 (Month 24) visit until the end of the third RSV season.

In the Revaccination Subcohorts B, C and D from 1st revaccination onwards and in Revaccination Subcohort 2A from d730 onwards, thrombosis with thrombocytopenia syndrome (TTS) is to be reported to the sponsor as an adverse event of special interest (AESI), within 24 hours of awareness. A potential AESI is defined as thrombotic events or symptomatic thrombocytopenia. For the analysis of serious AEs (SAEs) and (potential) AESIs in the Revaccination Cohorts the FAS will be used as well.

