For Revaccination Subcohort A, all SAEs will be reported from administration of study vaccine on Day 1 until the end of the first RSV season (or 6 months after vaccination, whichever comes later), and from the time of revaccination at Month 12 until the end of the second RSV season, or until 6 months after revaccination, whichever comes later. For Revaccination Subcohort 2A, all SAEs and AESIs will also be collected from the time of revaccination on Day 730 until 6 months after revaccination. For the other Revaccination Subcohorts (B, C, and D), SAEs and AESIs will be collected from the time of revaccination until 6 months thereafter. In addition, SAEs classified as related to the study vaccine, SAEs resulting in death, (S)AEs resulting in study discontinuation, and (S)AEs resulting from procedures and non-investigational (concomitant) Janssen products will be collected during the entire study for all participants. For the participants in the Revaccination Subcohorts C and D, these (S)AEs will be collected retrospectively for the time period between the last end of the RSV season visit and the revaccination upon the day of revaccination. For all Revaccination subcohorts, collection of SAEs associated with ARIs and complications related to ARIs that classify as SAEs will stop at the end of the second RSV

season for Subcohort A, on Day 730 (Month 24) for Subcohort B, and at the latest at the end of the third RSV season for Subcohorts C and D.

Different types of SAE tables will be created:

- one focusing on all FAS participants by period until the end of the study or until revaccination.
- one focusing on each Revaccination Subcohort, from revaccination onwards until the end of the study by period.

For related SAEs, SAES resulting in death and AEs leading to discontinuation, tables as described above or listings (depending on the number of occurrences) may be provided.

For AESI analyses, the following subcategories are defined:

- Potential AESIs as identified by the investigator in the database
- Potential AESIs selected programmatically. Those include all reported AEs that are identified by the selection rule:
  - SMQ (Standardised MedDRA Queries) = “EMBOLIC AND THROMBOTIC EVENTS (SMQ)”  
or
  - (SUB\_SMQ1 = “HAEMATOPOIETIC THROMBOCYTOPENIA (SMQ)” and SCOPE in (“BROAD”, “NARROW”)) or HLT (higher level term)=”Thrombocytopenias”
- Potential AESIs qualified for assessment  

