Potential AESIs (programmed/identified by the investigator) that have risk levels assessed by one of the following three criteria are considered ‘qualified for assessment’:
  - Brighton Collaboration Level (Level 1-5)
  - CDC Tier (non-tier 1/2, tier 1, tier 2)
  - PRAC criteria (confirmed, possible, probable, unlikely, criteria not met)

As AESI (potential, identified by the investigator and/or qualified for assessment) are only collected in the Revaccination Subcohorts B, C and D from 1st revaccination onwards and in Revaccination Subcohort 2A from Day 730 onwards, the analysis of these potential AESI will only include these cohorts/timepoints. Potential AESIs as identified by the investigator, will be tabulated according to the following categories: ‘Embolic and thrombotic events (SMQ; Standardised MedDRA Queries)’ and ‘Haematopoietic Thrombocytopenia (SMQ) (broad) or HLT (higher level term) = ‘Thrombocytopenias’, and ‘Other’. Potential AESI as identified by the investigator, related to study vaccine (investigator assessment), will be tabulated similarly. Potential AESIs qualified for assessment will be tabulated by categories: ‘Embolic and thrombotic events (SMQ)’ and ‘Haematopoietic Thrombocytopenia (SMQ) (broad) or HLT=Thrombocytopenias’.

In addition to the potential AESIs as identified by the investigator in the database, potential AESIs will also be selected programmatically. Those will be tabulated by categories: ‘Embolic

and thrombotic events (SMQ)' and 'Haematopoietic Thrombocytopenia (SMQ) (broad) or HLT=Thrombocytopenias'. Potential AESI determined programmatically, related to study vaccine (investigator assessment), will be tabulated similarly. For these, all cohorts and the whole study period will be included in the analyses.

All AESI analyses will be presented by phase as well as by time interval. The definition of the different time intervals can be found below.

Dose	Interval	From	to
Post-vaccination 1	0-28 days post-dose	Date time of the 1 st vaccination	Min of: * 
 
• 23:59 at the date of last contact (for discontinuations)
 
• 23:59 at date of DB cut-off for interim analyses
 
• Maximum (Date of Vaccination 1 + 28 days at 23:59 , date of scheduled visit 4 weeks after 1st vaccination at 23:59)
 

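### SAP Section 5.2 tabulates serious and non-serious programmatic potential AESIs together, by post-dose interval for all cohorts and the whole study, although their collection differs by cohort, dose and interval

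*SAP*

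**What the plan says.** Section 5.2 defines three kinds of potential AESI. For two of them, the investigator-identified and the qualified events, it states that they "are only collected in the Revaccination Subcohorts B, C and D from 1st revaccination onwards and in Revaccination Subcohort 2A from Day 730 onwards"; analysis of these two is limited to those cohorts and times. The third kind is selected by MedDRA query for thromboembolic events and thrombocytopenia: "Those include all reported AEs that are identified by the selection rule". For this kind the restriction is lifted: "For these, all cohorts and the whole study period will be included in the analyses". The layout is common to all three: "All AESI analyses will be presented by phase as well as by time interval". The intervals are 0-28 days, 29-56 days, 57 days to 6 months, and more than 6 months after each of up to three doses.

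The collection rules are elsewhere:

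- **Dose 1, non-serious (Section 4.2.1):** "unsolicited AEs within the 28-day period following the vaccination are collected only for the Safety Subset".
- **Dose 1, serious (Section 5.2):** "all SAEs will be reported from administration of study vaccine on Day 1 until the end of the first RSV season", or for 6 months if that is later. Afterwards only related, fatal, discontinuation, procedure- or product-related and ARI-linked events are collected.
- **Revaccination, unsolicited (Section 5.2):** "The analysis of solicited and unsolicited AEs will be restricted to the Revaccination Subcohorts".
- **Revaccination, Subcohorts B, C and D (Section 5.2):** "SAEs and AESIs will be collected from the time of revaccination until 6 months thereafter". Subcohort 2A has the same 6 months after its Day 730 dose.

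Section 4.2 gives the general denominator as all subjects in the population and period. Section 5.2 gives none specific to the programmatic AESIs.

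**The concern.** A database query finds only what was recorded. The same query run over all cohorts and intervals therefore returns nearly complete counts in some rows, serious events only in others, and a selected few in the latest rows. Nothing in Section 5.2 separates serious from non-serious events or marks the incomplete rows.

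This matters because every revaccination in Table 1 is active. There is no concurrent placebo group after doses 2 and 3, so a reader asking whether thrombotic or thrombocytopenic events are more common after revaccination will turn to the dose-1 rows. Those rows are the less complete ones. Late rows can also look empty because of the collection rules.

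**Working it through.** The SAP states no AESI rate, so there is no figure to reproduce. The check asks what share of true events can reach the table under the SAP's own rules.

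**Inputs**

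- Safety Subset: 350 + 350 = 700; randomised: 5,800 (Table 1). Share = 700/5,800 = 0.1207, or 12.1%.
- Denominator: all participants in the population and period. This is inferred from the general rule in Section 4.2 and the all-cohort wording in Section 5.2.
- s = share of events that are serious. The SAP does not give it, so it is assumed and varied.
- Planned Revaccination Subcohort sizes (Table 1): A 240, B 270, C 240, D 240, total 990; B + C + D = 750.
- Events meeting the query after revaccination are taken as fully captured while unsolicited AEs or AESIs are collected. True risk is taken as equal after each dose.

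**0-28 days.** Dose-1 capture = s + (1 - s) × 0.1207. Revaccination capture = 1. Apparent ratio = 1 / dose-1 capture.

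**Day 29 to 6 months.** Dose-1 capture = s, because only SAEs are collected. Capture in B, C and D = 1, because AESIs are collected as well as SAEs. Subcohort A has no AESI collection between Day 365 and Day 730, so its capture after dose 2 is also s. Pooled dose-2 capture = (240s + 750)/990.

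| Non-serious share (1 - s) | Dose-1 capture, 0-28 d | Ratio, 0-28 d | Ratio, 29 d-6 mo, B/C/D vs dose 1 | Ratio, 29 d-6 mo, pooled A-D vs dose 1 |
|---|---|---|---|---|
| 0% | 100% | 1.00 | 1.00 | 1.00 |
| 10% | 91% | 1.10 | 1.11 | 1.08 |
| 25% | 78% | 1.28 | 1.33 | 1.25 |
| 50% | 56% | 1.78 | 2.00 | 1.76 |
| 75% | 34% | 2.94 | 4.00 | 3.27 |

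Example at 50%: 0.50 + 0.50 × 0.1207 = 0.560, and 1/0.560 = 1.78. Within 6 months the ratio is never below 1 in this range.

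**Beyond 6 months.** The dose-1 row runs to last contact, cut-off or the second dose. Once the SAE window closes, an unrelated, non-fatal serious event with no link to an ARI falls outside the collection rules, unless it led to discontinuation or came from a procedure or concomitant product. The row is therefore understated even if every event is serious. The same applies after revaccination, where collection of all SAEs and AESIs in B, C and D ends at 6 months while the row continues. The size cannot be derived from the document. The dose-1 row is partly covered, because the first-season window may run past 6 months.

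**With matched collection.** Restricting to serious events within 6 months, or to 0-28 days with 700 as the dose-1 denominator, makes capture equal and the ratio 1.00 for every s.

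**The case against.** The programmatic search is an addition to the restricted analyses, a sweep so that no reported event is missed. No dose-to-dose comparison is planned, and Section 4.2 rules out formal comparisons between groups. Sections 2.3.1 and 4.2.1.1 already tie unsolicited AEs after Day 1 to the Safety Subset and SAEs to the FAS, so the 5,800 denominator is not stated anywhere for this table. The serious share has no source in the SAP, and a footnote on collection windows might be enough.

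Much of this stands. The denominator is an inference, and the ratio is 1.0 if all events are serious. But separate denominators for unsolicited AEs and for SAEs do not settle a table that pools both, and without a planned comparison the descriptive rates are what readers will use. A footnote would warn the reader but would leave the percentages incomparable.

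Three stronger readings are tempting but not supported:

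- **That revaccination is made to look riskier than it is.** Its rates are not inflated; the distortion is only relative to dose 1.
- **That these events are collected only in some cohorts.** That sentence concerns investigator-identified and qualified AESIs. Serious events are collected in all participants early after dose 1, and related, fatal and discontinuation events throughout the study.
- **That the IDMC is misled.** Section 3.1 lists Sections 4.2, 4.4.1 and 4.4.2 for its analyses, not 5.2.

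**Conclusion.** The point holds in a limited form. As written, Section 5.2 produces interval rows with unequal capture and does not say so. If percentages use all participants in the population and period, non-serious events after dose 1 and all events beyond 6 months are understated relative to early post-revaccination rows. At 0-28 days the apparent revaccination/dose-1 ratio under equal true risk runs from 1.0 to 2.9 for a non-serious share of 0% to 75%. That share is assumed, so this is a range of possible distortion and not an estimate. The active-placebo contrast after dose 1 follows the same rules in both arms. The change should be made because it is cheap and extends what the SAP already does: Section 4.2.1.1 lists non-serious AEs from outside the window or subset, and the end of Section 5.2 bases solicited-AE percentages on participants with assessed data.

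**What to change.** Keep the all-cohort programmatic search and amend Section 5.2 as follows:

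- (a) Tabulate serious potential AESIs separately in the FAS for 0-28 days, 29-56 days and 57 days to 6 months after each dose.
- (b) Tabulate all potential AESIs, including non-serious ones, for 0-28 days, with the Safety Subset as denominator after dose 1 and the Revaccination Subcohorts after doses 2 and 3.
- (c) Show events outside these windows or subsets, including those beyond 6 months, as counts or a listing without percentages, flagged as incompletely collected.
- (d) Reconcile the two statements in Section 5.2 on AESI collection after revaccination, one ending at 6 months and the other open-ended.

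The cost is SAP wording and table shells; no new data are needed. The downside is a smaller dose-1 denominator for non-serious events, 700 instead of 5,800.

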### 2.1.2. Immunogenicity Visit Windows

For immunogenicity summaries and tabulations per time point, assessments will be allocated to an analysis visit based on the planned visit as captured in the CRF. Visits that are out of the protocol-defined visit windows (see table below) will not be included in the immunogenicity summaries and tabulations per timepoint. However, they may be included in sensitivity analyses.

Analysis timepoint	Subset	Reference day	Target day (counted from the reference day)	Window
Baseline	Immuno Subset / All Revaccination Subcohorts	Day of vaccination 1	1	(-inf, 1]
Day 15	Immuno Subset / All Revaccination Subcohorts	Day of vaccination 1	15	[15, 18]
Day 85	Immuno Subset	Day of vaccination 1	85	[78, 92]
Day 169	Immuno Subset	Day of vaccination 1	169	[155, 183]
Day 365	Immuno Subset / Revaccination Subcohort 1B, 2B, 1C, 2C, 1D and 2D	Day of vaccination 1	365	[304, 426]
Day 365	Revaccination Subcohorts 1A, 2A	Day of vaccination 2	1	[1]
Day 379	Revaccination Subcohorts 1A, 2A	Day of vaccination 2	15	[15, 18]
Day 393	Revaccination Subcohorts 1A, 2A	Day of vaccination 2	29	[29, 32]
Day 449	Revaccination Subcohorts 1A, 2A	Day of vaccination 2	85	[78, 92]
Day 533	Immuno Subset	Day of vaccination 1	533	[519, 547]
Day 533	Revaccination Subcohorts 1A, 2A	Day of vaccination 2	169	[155, 183]
Day 730	Immuno Subset	Day of vaccination 1	730	[669, 791]
Day 730	Revaccination Subcohort 1A	Day of vaccination 2	365	[334,396]
Day 730	Revaccination Subcohort 1B, 2B	Day of vaccination 2	1	[1]
Day 730	Revaccination Subcohort 2A	Day of vaccination 3	1	[1]
Day 737	Revaccination Subcohort 1B, 2B	Day of vaccination 2	8	[6, 10]
Day 737	Revaccination Subcohort 2A	Day of vaccination 3	8	[6, 10]
Day 744	Revaccination Subcohort 1B, 2B	Day of vaccination 2	15	[15, 18]
Day 744	Revaccination Subcohort 2A	Day of vaccination 3	15	[15, 18]
Day 758	Revaccination	Day of vaccination 2	29	[29, 32]

Analysis timepoint	Subset	Reference day	Target day (counted from the reference day)	Window
	Subcohort 1B, 2B			
Day 758	Revaccination Subcohort 2A	Day of vaccination 3	29	[29, 32]
Day 814	Revaccination Subcohort 1B, 2B	Day of vaccination 2	85	[78, 92]
Day 814	Revaccination Subcohort 2A	Day of vaccination 3	85	[78, 92]
Day 898	Revaccination Subcohort 1B, 2B	Day of vaccination 2	169	[155, 183]
Day 898	Revaccination Subcohort 2A	Day of vaccination 3	169	[155, 183]

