	29-56 days post-dose	One minute after the end of the interval 0-28 days post dose	Min of: 
 
• 23:59 at date of last contact (for discontinuations)
 
• 23:59 at date of DB cut-off for interim analyses
 
• Date of Vaccination 1 + 56 days at 23:59
 

	57 days - 6 months post-dose	One minute after the end of the interval 29-56 days post-dose	Min of: 
 
• 23:59 at date of last contact (for discontinuations)
 
• 23:59 at date of DB cut-off for interim analyses
 
• Maximum (Date of Vaccination 1 + 168 days at 23:59 , date of scheduled visit 168 days post 1st vaccination at 23:59 )
 

	>6 months post-dose	One minute after the end of the interval 57 days - 6 months post-dose	Min of: 
 
• 23:59 at the date of last contact (for discontinuations)
 
• 23:59 at the date of DB cut-off for interim analyses
 
• 1 min prior to date time of vaccination 2 for participants in the Revaccination Subcohorts
 

Post-vaccination	0-28 days	Date time of the	Min of: *

2	post-dose	2 nd vaccination	
 
• 23:59 at the date of last contact (for discontinuations)
 
• 23:59 at date of DB cut-off for interim analyses
 
• Maximum (Date of Vaccination 2 + 28 days at 23:59 , date of scheduled visit 4 weeks after 2nd vaccination at 23:59 )
 

	29-56 days post-dose	One minute after the end of the interval 0-28 days post-dose	Min of: 
 
• 23:59 at date of last contact (for discontinuations)
 
• 23:59 at date of DB cut-off for interim analyses
 
• Date of vaccination 2 + 56 days at 23:59
 

	57 days - 6 months post-dose	One minute after the end of the interval 29-56 days post-dose	Min of: 
 
• 23:59 at date of last contact (for discontinuations)
 
• 23:59 at date of DB cut-off for interim analyses
 
• Maximum(Date of vaccination 2 + 168 days at 23:59 , Day 533 visit at 23:59)
 

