	>6 months post-dose	One minute after the end of the interval 57 days - 6 months post-dose	Min of: 
 
• 23:59 at the date of last contact (for discontinuations)
 
• 23:59 at the date of DB cut-off for interim analyses
 
• 1 min prior to date time of vaccination 3 at 23:59 for participants in Revaccination Subcohorts 2A and 2B
 

Post-vaccination 3	0-28 days post-dose	Date time of the 3 rd vaccination	Min of:* 
 
• 23:59 at the date of last contact (for discontinuations)
 
• 23:59 at date of DB cut-off for interim analyses
 
• Maximum(Date of vaccination 3 + 28 days at 23:59 , date of scheduled visit 4 weeks after 3rd vaccination at 23:59 )
 

	29-56 days post-dose	One minute after the end of the interval 0-28 days post-dose	Min of: 
 
• 23:59 at date of last contact (for discontinuations)
 
• 23:59 at date of DB cut-off for
 

			interim analyses 
 
• Date of vaccination 3 + 56 days at 23:59
 

	57 days - 6 months post-dose	One minute after the end of the interval 29-56 days post-dose	Min of: 
 
• 23:59 at date of last contact (for discontinuations)
 
• 23:59 at date of DB cut-off for interim analyses
 
• Maximum(Date of vaccination 3 + 168 days at 23:59 , Day 898 visit at 23:59 )
 

	>6 months post-dose	One minute after the end of the interval 57 days - 6 months post-dose	Min of: 
 
• 23:59 at the date of last contact (for discontinuations)
 
• 23:59 at the date of DB cut-off for interim analyses
 

The combination of the '0 - 28 days post-dose' interval and the '29 - 56 days post-dose' interval will be referred as '0 - 56 days post-dose'.

The combination of the '0 - 28 days post-dose' , '29 - 56 days post-dose' and '57 days - 6 months post-dose' intervals will be referred as '0-6 months post-dose'.

\*In case the '0 - 28 days post-dose' interval ends later than 56 days post vaccination then the '29 - 56 days post-dose' interval is not required. For example, if a participant had Day 29 visit at relative day 57, then the following intervals will be created:

0 - 28 days post-dose, lasting from 0 to relative day 57,

57 days - 6 months post-dose, lasting from 58 onwards.

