In case the definitions of the time intervals cause overlap, the start date of the latter time interval should always start one minute after the end of the previous one.

For potential AESIs qualified for assessment, potential AESIs as identified by the investigator and potential AESIs determined programmatically, attribution to the intervals will be done similarly to the unsolicited AEs as described in Section 4.2.1.3. For Step 2 of phase allocation of adverse events, the '0 - 28 days post-dose' interval should be treated similar to 'active' periods and the rest as 'non- active' periods.

Further, for solicited AEs, the denominator for the percentages will be the number of participants with data assessed by the PI in the considered population and phase for a certain regimen (incidence per 100 participants/phase) and risk level.

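### In the Section 5.2 AESI interval table, the Day 533 and Day 898 visits that close the 57 days to 6 months interval fit only Subcohort A (dose 2) and 2A (dose 3), and one further end point contradicts itself

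*SAP*

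**What the plan says.** Section 5.2 presents all AESI analyses by phase and by time interval since each dose. In the interval table, 57 days to 6 months ends at the earliest of last contact, database cut-off and a third term. That third term differs by row:

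- After vaccination 1 it is the later of dose + 168 days and the "date of scheduled visit 168 days post 1 st vaccination at 23:59".
- After vaccination 2 it is "Maximum(Date of vaccination 2 + 168 days at 23:59 , Day 533 visit at 23:59".
- After vaccination 3 it is "Maximum(Date of vaccination 3 + 168 days at 23:59 , Day 898 visit at 23:59".

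No row distinguishes subcohorts. The visit table in Section 2.1.2 does: "Day 533 Revaccination Subcohorts 1A, 2A Day of vaccination 2 169 [155, 183" is one row and "Day 898 Revaccination Subcohort 1B, 2B Day of vaccination 2 169 [155, 183" another.

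On who contributes events, Section 5.2 says that investigator-identified and qualified AESIs "are only collected in the Revaccination Subcohorts B, C and D from 1st revaccination onwards", and in 2A from Day 730. Programmatically selected AESIs cover all cohorts and the whole study.

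The dose-2 interval beyond 6 months ends "1 min prior to date time of vaccination 3 at 23:59 for participants in Revaccination Subcohorts 2A and 2B". Where intervals overlap, "the start date of the latter time interval should always start one minute after the end of the previous one".

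**The concern.** The dose-1 row, and the 0 to 28 day rows for all three doses, refer generically to a visit at a set time after that dose. Only the two 6-month cells for doses 2 and 3 carry a fixed study-day label, and each label belongs to one revaccination schedule. Applied to everyone, the cell works as intended in one group and does nothing in the others. The upper limit of the interval, and of the combined 0 to 6 months interval built from it, then depends on the subcohort.

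The stray clock time raises a different question: to which dose an event on the day of vaccination 3 is attributed. In a table that supports the assessment of thrombosis with thrombocytopenia, both the interval and the dose should be unambiguous.

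**Working it through.** **Inputs.** Nominal dose days come from Table 1 and the visit table in Section 2.1.2: dose 2 on Day 365 (A), 730 (B), 1095 (C) and 1460 (D); dose 3 on Day 730 (2A) and 1095 (2B). The 6-month visit has target relative day 169 and window [155, 183], with the dose day counted as day 1. The target is therefore dose + 168 days and the latest in-window visit is dose + 182.

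**Reproducing the SAP's labels** (nominal visit = dose day + 168):

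| Dose | Subcohort | Own 6-month visit | Visit named in Section 5.2 |
|---|---|---|---|
| 2 | A | 365 + 168 = 533 | 533 (matches) |
| 2 | B | 730 + 168 = 898 | 533 |
| 2 | C | 1095 + 168 = 1263 | 533 |
| 2 | D | 1460 + 168 = 1628 | 533 |
| 3 | 2A | 730 + 168 = 898 | 898 (matches) |
| 3 | 2B | 1095 + 168 = 1263 | 898 |

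The computed days agree with the visit table in every row. Day 898 is also B's visit 168 days after dose 2, but Section 5.2 does not use it there. Day 533 is also an Immuno Subset visit, counted from vaccination 1.

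**The visit term cannot operate in the unmatched rows.** Take the earliest plausible dosing, assuming the Immuno Subset's Day 730 window [669, 791] also bounds the revaccination date. Subcohort B then reaches dose 2 + 168 at Day 669 + 168 = 837, after the latest in-window Day 533 visit (547). For 2B, assume dose 3 as early as 1095 − 61 = Day 1034. Then 1034 + 168 = 1202, after the latest Day 898 visit (791 + 182 = 973). C and D are dosed later still. The maximum therefore reduces to dose + 168 in B, C, D (dose 2) and 2B (dose 3).

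**End of the interval by lateness of the participant's own visit:**

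| Own visit | A (dose 2), 2A (dose 3) | B, C, D (dose 2), 2B (dose 3) | Difference |
|---|---|---|---|
| On or before target | dose + 168 | dose + 168 | 0 days |
| 7 days late | dose + 175 | dose + 168 | 7 days |
| 14 days late | dose + 182 | dose + 168 | 14 days |

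The in-window maximum is 182 − 168 = 14 days, or 14/182 = 7.7% of the interval from dose to that visit. If visits were spread evenly over the 29-day window (an assumption), the mean shift would be (1 + 2 + … + 14)/29 = 105/29, about 3.6 days.

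**Which events can be binned differently.** The events concerned have onset at dose + 169 to dose + 182, on or before a late 6-month visit.

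- Programmatically selected AESIs, after dose 2: A versus B, C and D.
- Collected AESIs, after dose 3: 2A versus 2B.
- The effective dose-2 rule in B, C and D also differs from the rule written for dose 1, which follows the participant's own visit where one is scheduled. For collected AESIs this is a difference in rule only, because their collection starts at revaccination.

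**The second end point.** The post-dose-3 interval starts at the date and time of vaccination 3. Read as 23:59 on that day, the end of the dose-2 interval overlaps it. The overlap rule then starts the dose-3 interval one minute later, on the next day, so events on the day of dose 3 fall in the dose-2 interval beyond 6 months. Section 5.2 treats that interval as non-active. The other reading, one minute before the injection, gives no overlap. The phrase states both times.

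**The case against.** The strongest reply is that little turns on this.

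- A reader might infer that collected AESIs are binned differently across subcohorts after dose 2. They are not. Investigator-identified and qualified AESIs after dose 2 come only from B, C and D, and all three end at dose + 168. The contrast with A exists only for programmatically selected AESIs.
- A reader might also infer that the 0 to 6 months counts are too low in B, C and D. The SAP does not support that. Dose + 168 is its own nominal boundary in every row, and AESI collection in these subcohorts is planned to run until 6 months after revaccination. What can be shown is an inconsistent upper limit, not a deficit.
- Fourteen days is the extreme for in-window visits. It should not be applied to all 2 × 135 + 4 × 120 = 750 planned dose-2 recipients in B, C and D. Of these, 480 are in C and D, which proceed only if the Subcohort B results support it.
- The 0 to 28 and 29 to 56 day intervals after each dose do not use the labels, phase presentations are unaffected, and Section 4.2, which Section 5.2 follows, plans no formal comparison between groups.
- The intended meaning of the 23:59 phrase can be recovered from the parallel dose-1 row, which has no clock time, and from Table 2, which ends follow-up one minute before revaccination.

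All of this stands, and it limits the point to a minor one. It does not make the two cells correct: as written, they apply a visit label to subcohorts in which it cannot work, and a programmer following the text would implement that.

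**Conclusion.** Wrong as written; minor. The visit term has no effect for B, C and D after dose 2 or for 2B after dose 3, whose interval always ends at dose + 168 days. It can extend to dose + 182 for in-window visits in A (dose 2), in 2A (dose 3) and under the generic dose-1 rule. The resulting shift ranges from 0 to 14 days at one boundary of a descriptive safety table. Visits held after the window could widen it, since Section 5.2 does not restrict the term to in-window visits. The dose + 168 term keeps the interval defined, and no event is lost.

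The 23:59 phrase is a separate self-contradiction. It matters only under the literal reading, and only for the planned 120 participants of 2A and 135 of 2B who are due a third dose.

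The result rests on the dose days and windows in the SAP's own visit table and, for the check on early dosing, on the assumed 61-day allowance.

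**What to change.** In the 57 days to 6 months cells for vaccinations 2 and 3, replace the Day 533 and Day 898 labels with the dose-1 form: the date of the scheduled visit 168 days after the second or third vaccination, respectively. For the derivation, this means Day 533 (A), 898 (B), 1263 (C) and 1628 (D) after dose 2, and Day 898 (2A) and 1263 (2B) after dose 3. Keep dose + 168 days as the other term of the maximum.

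In the dose-2 interval beyond 6 months, delete the clock time so that the interval ends one minute before the date and time of vaccination 3.

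The cost is two table cells and one phrase in the SAP, plus the matching lines of derivation code. No data collection changes.
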